#### **8.3.1. Time Period and Frequency for Collecting AE and SAE Information**

The time period for actively eliciting and collecting AEs and SAEs (“active collection period”) for each participant begins from the time the participant provides informed consent, which is obtained before the participant’s participation in the study (ie, before undergoing any study-related procedure and/or receiving study intervention), through and including a minimum of 28 calendar days, except as indicated below, after the last administration of the study intervention.

Follow-up by the investigator continues throughout and after the active collection period and until the AE or SAE or its sequelae resolve or stabilize at a level acceptable to the investigator.

For participants who are screen failures, the active collection period ends when screen failure status is determined.

If the participant withdraws from the study and also withdraws consent for the collection of future information, the active collection period ends when consent is withdrawn.

If a participant permanently discontinues or temporarily discontinues study intervention because of an AE or SAE, the AE or SAE must be recorded on the CRF and the SAE reported using the CT SAE Report Form.

Investigators are not obligated to actively seek information on AEs or SAEs after the participant has concluded study participation. However, if the investigator learns of any SAE, including a death, at any time after a participant has completed the study, and he/she

considers the event to be reasonably related to the study intervention, the investigator must promptly report the SAE to Pfizer using the CT SAE Report Form.

### **8.3.1.1. Reporting SAEs to Pfizer Safety**

All SAEs occurring in a participant during the active collection period as described in [Section 8.3.1](#) are reported to Pfizer Safety on the CT SAE Report Form immediately upon awareness and under no circumstance should this exceed 24 hours, as indicated in [Appendix 3](#). The investigator will submit any updated SAE data to the sponsor within 24 hours of it being available.

### **8.3.1.2. Recording Nonserious AEs and SAEs on the CRF**

All nonserious AEs and SAEs occurring in a participant during the active collection period, which begins after obtaining informed consent as described in [Section 8.3.1](#), will be recorded on the AE section of the CRF.

The investigator is to record on the CRF all directly observed and all spontaneously reported AEs and SAEs reported by the participant.

Reporting of AEs and SAEs for participants who fail screening are subject to the CRF requirements as described in [Section 5.4](#).

### **8.3.2. Method of Detecting AEs and SAEs**

The method of recording, evaluating, and assessing causality of AEs and SAEs and the procedures for completing and transmitting SAE reports are provided in [Appendix 3](#).

Care will be taken not to introduce bias when detecting AEs and/or SAEs. Open-ended and nonleading verbal questioning of the participant is the preferred method to inquire about AE occurrences.

### **8.3.3. Follow-Up of AEs and SAEs**

After the initial AE or SAE report, the investigator is required to proactively follow each participant at subsequent visits/contacts. For each event, the investigator must pursue and obtain adequate information until resolution, stabilization, the event is otherwise explained, or the participant is lost to follow-up (as defined in [Section 7.3](#)).

In general, follow-up information will include a description of the event in sufficient detail to allow for a complete medical assessment of the case and independent determination of possible causality. Any information relevant to the event, such as concomitant medications and illnesses, must be provided. In the case of a participant death, a summary of available autopsy findings must be submitted as soon as possible to Pfizer Safety.

Further information on follow-up procedures is given in [Appendix 3](#).

### **8.3.4. Regulatory Reporting Requirements for SAEs**

Prompt notification by the investigator to the sponsor of an SAE is essential so that legal obligations and ethical responsibilities toward the safety of participants and the safety of a study intervention under clinical investigation are met.

The sponsor has a legal responsibility to notify both the local regulatory authority and other regulatory agencies about the safety of a study intervention under clinical investigation. The sponsor will comply with country-specific regulatory requirements relating to safety reporting to the regulatory authority, IRBs/ECs, and investigators.

Investigator safety reports must be prepared for SUSARs according to local regulatory requirements and sponsor policy and forwarded to investigators as necessary.

An investigator who receives SUSARs or other specific safety information (eg, summary or listing of SAEs) from the sponsor will review and then file it along with the SRSD(s) for the study and will notify the IRB/EC, if appropriate according to local requirements.

### **8.3.5. Environmental Exposure, Exposure During Pregnancy or Breastfeeding, and Occupational Exposure**

Environmental exposure occurs when a person not enrolled in the study as a participant receives unplanned direct contact with or exposure to the study intervention. Such exposure may or may not lead to the occurrence of an AE or SAE. Persons at risk for environmental exposure include healthcare providers, family members, and others who may be exposed. An environmental exposure may include exposure during pregnancy, exposure during breastfeeding, and occupational exposure.

Any such exposure to the study intervention under study are reportable to Pfizer Safety within 24 hours of investigator awareness.

#### **8.3.5.1. Exposure During Pregnancy**

An EDP occurs if:

- A female participant is found to be pregnant while receiving or after discontinuing study intervention.
- A male participant who is receiving or has discontinued study intervention exposes a female partner prior to or around the time of conception.
- A female is found to be pregnant while being exposed or having been exposed to study intervention due to environmental exposure. Below are examples of environmental EDP:
  - A female family member or healthcare provider reports that she is pregnant after having been exposed to the study intervention by ingestion.

- A male family member or healthcare provider who has been exposed to the study intervention by ingestion then exposes his female partner prior to or around the time of conception.

The investigator must report EDP to Pfizer Safety within 24 hours of the investigator's awareness, irrespective of whether an SAE has occurred. The initial information submitted should include the anticipated date of delivery (see below for information related to termination of pregnancy).

- If EDP occurs in a participant or a participant's partner, the investigator must report this information to Pfizer Safety on the CT SAE Report Form and an EDP Supplemental Form, regardless of whether an SAE has occurred. Details of the pregnancy will be collected after the start of study intervention and until 28 days after the last dose.
- If EDP occurs in the setting of environmental exposure, the investigator must report information to Pfizer Safety using the CT SAE Report Form and EDP Supplemental Form. Since the exposure information does not pertain to the participant enrolled in the study, the information is not recorded on a CRF; however, a copy of the completed CT SAE Report Form is maintained in the investigator site file.

Follow-up is conducted to obtain general information on the pregnancy and its outcome for all EDP reports with an unknown outcome. The investigator will follow the pregnancy until completion (or until pregnancy termination) and notify Pfizer Safety of the outcome as a follow-up to the initial EDP Supplemental Form. In the case of a live birth, the structural integrity of the neonate can be assessed at the time of birth. In the event of a termination, the reason(s) for termination should be specified and, if clinically possible, the structural integrity of the terminated fetus should be assessed by gross visual inspection (unless preprocedure test findings are conclusive for a congenital anomaly and the findings are reported).

Abnormal pregnancy outcomes are considered SAEs. If the outcome of the pregnancy meets the criteria for an SAE (ie, ectopic pregnancy, spontaneous abortion, intrauterine fetal demise, neonatal death, or congenital anomaly in a live-born baby, a terminated fetus, an intrauterine fetal demise, or a neonatal death), the investigator should follow the procedures for reporting SAEs. Additional information about pregnancy outcomes that are reported to Pfizer Safety as SAEs follows:

- Spontaneous abortion including miscarriage and missed abortion;
- Neonatal deaths that occur within 1 month of birth should be reported, without regard to causality, as SAEs. In addition, infant deaths after 1 month should be reported as SAEs when the investigator assesses the infant death as related or possibly related to exposure to the study intervention.

Additional information regarding the EDP may be requested by the sponsor. Further follow-up of birth outcomes will be handled on a case-by-case basis (eg, follow-up on preterm infants to identify developmental delays). In the case of paternal exposure, the investigator will provide the participant with the Pregnant Partner Release of Information Form to deliver to his partner. The investigator must document in the source documents that the participant was given the Pregnant Partner Release of Information Form to provide to his partner.

### **8.3.5.2. Exposure During Breastfeeding**

An exposure during breastfeeding occurs if:

- A female participant is found to be breastfeeding while receiving or after discontinuing study intervention.
- A female is found to be breastfeeding while being exposed or having been exposed to study intervention (ie, environmental exposure). An example of environmental exposure during breastfeeding is a female family member or healthcare provider who reports that she is breastfeeding after having been exposed to the study intervention by ingestion.

The investigator must report exposure during breastfeeding to Pfizer Safety within 24 hours of the investigator's awareness, irrespective of whether an SAE has occurred. The information must be reported using the CT SAE Report Form. When exposure during breastfeeding occurs in the setting of environmental exposure, the exposure information does not pertain to the participant enrolled in the study, so the information is not recorded on a CRF. However, a copy of the completed CT SAE Report Form is maintained in the investigator site file.

An exposure during breastfeeding report is not created when a Pfizer drug specifically approved for use in breastfeeding women (eg, vitamins) is administered in accord with authorized use. However, if the infant experiences an SAE associated with such a drug, the SAE is reported together with the exposure during breastfeeding.

### **8.3.5.3. Occupational Exposure**

The investigator must report any instance of occupational exposure to Pfizer Safety within 24 hours of the investigator's awareness using the CT SAE Report Form regardless of whether there is an associated SAE. Since the information about the occupational exposure does not pertain to a participant enrolled in the study, the information is not recorded on a CRF; however, a copy of the completed CT SAE Report Form must be maintained in the investigator site file.

### **8.3.6. Cardiovascular and Death Events**

Not applicable.

### **8.3.7. Disease-Related Events and/or Disease-Related Outcomes Not Qualifying as AEs or SAEs**

Not applicable.

### **8.3.8. Adverse Events of Special Interest**

Adverse events of special interest (AESIs) are examined as part of routine safety data review procedures throughout the clinical trial and as part of signal detection processes.

All AESIs must be reported as an AE or SAE following the procedures described in [Section 8.3.1](#) through [8.3.4](#). An AESI is to be recorded as an AE or SAE on the CRF. In addition, an AESI that is also an SAE must be reported using the CT SAE Report Form.

#### **8.3.8.1. Lack of Efficacy**

This section is not applicable because efficacy is not expected in the study population.

### **8.3.9. Medical Device Deficiencies**

Not applicable.

### **8.3.10. Medication Errors**

Medication errors may result from the administration or consumption of the study intervention by the wrong participant, or at the wrong time, or at the wrong dosage strength.

Exposures to the study intervention under study may occur in clinical trial settings, such as medication errors.

Safety Event	Recorded on the CRF	Reported on the CT SAE Report Form to Pfizer Safety Within 24 Hours of Awareness
Medication errors	All (regardless of whether associated with an AE)	Only if associated with an SAE

Medication errors include:

- Medication errors involving participant exposure to the study intervention;
- Potential medication errors or uses outside of what is foreseen in the protocol that do or do not involve the study participant.

Such medication errors occurring to a study participant are to be captured on the medication error page of the CRF, which is a specific version of the AE page.

In the event of a medication dosing error, the sponsor should be notified within 24 hours.

Whether or not the medication error is accompanied by an AE, as determined by the investigator, the medication error is recorded on the medication error page of the CRF and, if applicable, any associated AE(s), serious and nonserious, are recorded on the AE page of the CRF.

Medication errors should be reported to Pfizer Safety within 24 hours on a CT SAE Report Form **only when associated with an SAE**.

## 8.4. Pharmacokinetics

### 8.4.1. Plasma for Analysis of PF-07321332

Blood samples of approximately 4 mL, to provide approximately 1.5 mL plasma, will be collected for measurement of plasma concentrations of PF-07321332 as specified in the [SoA](#). Instructions for the collection and handling of biological samples will be provided in the laboratory manual or by the sponsor. The actual date and time (24-hour clock time) of each sample will be recorded.

The actual times may change, but the number of samples will remain the same. All efforts will be made to obtain the samples at the exact nominal time relative to dosing. Collection of samples up to and including 10 hours after dose administration that are obtained within 10% of the nominal time relative to dosing (eg, within 6 minutes of a 60-minute sample) will not be captured as a protocol deviation, as long as the exact time of the collection is noted on the source document and the CRF. Collection of samples more than 10 hours after dose administration that are obtained  $\leq$ 1 hour away from the nominal time relative to dosing will not be captured as a protocol deviation, as long as the exact time of the collection is noted on the source document and the CRF.

Samples will be used to evaluate the PK of PF-07321332. Samples collected for analyses of plasma PF-07321332 concentration may also be used to evaluate safety or efficacy aspects related to concerns arising during or after the study, for metabolite identification and/or evaluation of the bioanalytical method, **CCI** [REDACTED]

**CCI**  
[REDACTED]

Samples collected for measurement of plasma concentrations of PF-07321332 will be analyzed using a validated analytical method in compliance with applicable SOPs. Potential metabolites may be analyzed with either validated or exploratory methods.

The PK samples must be processed and shipped as indicated in the instructions provided to the investigator site to maintain sample integrity. Any deviations from the PK sample handling procedure (eg, sample collection and processing steps, interim storage or shipping conditions), including any actions taken, must be documented and reported to the sponsor. On a case-by-case basis, the sponsor may make a determination as to whether sample integrity has been compromised.

Any changes in the timing or addition of time points for any planned study assessments must be documented and approved by the relevant study team member and then archived in the sponsor and site study files, but will not constitute a protocol amendment. The IRB/EC will be informed of any safety issues that require alteration of the safety monitoring scheme or amendment of the ICD.

CCI

CCI

## 8.7. Immunogenicity Assessments

Immunogenicity assessments are not included in this study.

## 8.8. Health Economics

Health economics/medical resource utilization and health economics parameters are not evaluated in this study.

## 9. STATISTICAL CONSIDERATIONS

Detailed methodology for summary and statistical analyses of the data collected in this study is outlined here and further detailed in a SAP, which will be maintained by the sponsor. The SAP may modify what is outlined in the protocol where appropriate; however, any major modifications of the primary endpoint definitions or their analyses will also be reflected in a protocol amendment.

### 9.1. Statistical Hypotheses

No statistical hypothesis will be tested in this study.

### 9.2. Analysis Sets

For purposes of analysis, the following analysis sets are defined:

Participant Analysis Set	Description
Enrolled/Randomly assigned to study intervention	“Enrolled” means a participant’s, agreement to participate in a clinical study following completion of the informed consent process and screening. Potential participants who are screened for the purpose of determining eligibility for the study, but do not participate in the study, are not considered enrolled, unless otherwise specified by the protocol. A participant will be considered enrolled if the informed consent is not withdrawn prior to participating in any study activity after screening.
Safety Analysis Set	All participants randomly assigned to study intervention and who take at least 1 dose of study intervention. Participants will be analyzed according to the product they actually received.

Participant Analysis Set	Description
PK Concentration Set	All participants randomly assigned to study intervention and who take at least 1 dose of study intervention and in whom at least 1 concentration value is reported.
PK Parameter Set	All participants randomly assigned to study intervention and who take at least 1 dose of study intervention and in whom at least 1 of the PK parameters of interest are reported.

### 9.3. Statistical Analyses

The SAP will be developed and finalized before any analyses are performed and will describe the analyses and procedures for accounting for missing, unused, and spurious data. This section is a summary of the planned statistical analyses of the primary and secondary endpoints.

#### 9.3.1. Primary Endpoint(s)

##### 9.3.1.1. Derivation of Pharmacokinetic Parameters

Plasma PK parameters of PF-07321332 will be derived (as data permit) from the concentration-time data using standard noncompartmental methods as outlined in the [Table 2](#). Actual PK sampling times will be used in the derivation of PK parameters. In the case that actual PK sampling times are not available, nominal PK sampling time will be used in the derivation of PK parameters.

**Table 2. Plasma PF-07321332 PK Parameters Definitions**

Parameter	Definition	Method of Determination
AUC inf *	Area under the plasma concentration-time curve from time zero extrapolated to infinity	AUC last + (C last */k el ), where C last * is the predicted plasma concentration at the last quantifiable time point from the log-linear regression analysis
AUC last	Area under the plasma concentration-time profile from time zero to the time of the last quantifiable concentration (C last ).	Linear/Log trapezoidal method.
C max	Maximum observed plasma concentration	Observed directly from data
T max	Time to reach C max	Observed directly from data as time of first occurrence
t 1/2 *	Terminal elimination half-life	Log e (2)/k el , where k el is the terminal phase rate constant calculated by a linear regression of the loglinear concentration-time curve. Only those data points judged to describe the terminal loglinear decline will be used in the regression.
CL/F*	Apparent clearance	Dose/AUC inf
V d /F*	Apparent volume of distribution for extravascular dosing	Dose/(AUC inf • k el )

\*If data permit.

### 9.3.1.2. Statistical Methods for Pharmacokinetic Data

Natural log transformed AUCinf (if data permit), AUClast and Cmax will be analyzed using a mixed effect model with sequence, period and treatment as fixed effects and participant within sequence as a random effect. Estimates of the adjusted mean differences (Test-Reference) and corresponding 90% CIs will be obtained from the model. The adjusted mean differences and 90% CIs for the differences will be exponentiated to provide estimates of the ratio of adjusted geometric means (Test/Reference) and 90% CI for the ratios. Treatment A (PF-07321332/ritonavir administered under fasted condition) is the Reference treatment and Treatment B (PF-07321332/ritonavir administered under fed condition) is the Test treatment.

The plasma concentrations of PF-07321332 will be listed and descriptively summarized by nominal PK sampling time and treatment. Individual participant, as well as mean and median profiles of the plasma concentration time data will be plotted by treatment using actual (for individual) and nominal (for mean and median) times respectively. Mean and median profiles will be presented on both linear and semi-log scales.

The PK parameters listed in Table 2 will be summarized descriptively by treatment.

Additional specifications about the tables, listings, and figures will be outlined in the SAP.

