## 3. OBJECTIVES AND ENDPOINTS

Objectives	Endpoints
Primary: 

To evaluate the effect of a high-fat meal on the exposure of PF-07321332 boosted with ritonavir following a single oral dose of PF-07321332 in combination with ritonavir using 150 mg tablet formulation of PF-07321332.

	Primary: 

The ratio of <math>AUC_{last}</math>, <math>AUC_{inf}</math> (if data permit) and <math>C_{max}</math> of PF-07321332.

Secondary: 

To characterize the pharmacokinetic parameters of PF-07321332 boosted with ritonavir following a single oral dose of PF-07321332 in combination with ritonavir.

To evaluate the safety and tolerability of PF-07321332/ritonavir in healthy participants.

	Secondary: 

<math>T_{max}</math>, and <math>t_{1/2}</math>, <math>CL/F</math> and <math>V/F</math> (if data permit).

Assessment of TEAEs, clinical laboratory abnormalities, vital signs, and 12-lead ECGs.

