## 4. STUDY DESIGN

### 4.1. Overall Design

This is a Phase 1, open-label, single dose, randomized, 2-treatment, 2-sequence, 2-period crossover study to evaluate the effect of a high-fat meal on the relative bioavailability of PF-07321332 boosted with ritonavir following single dose oral administration of PF-07321332 in combination with ritonavir using 150 mg tablet formulation of PF-07321332 in healthy adult participants. The study will consist of 2 treatments: a single oral dose of 300 mg PF-07321332 (2 × 150 mg tablets) under fasted conditions and 3 doses of 100 mg ritonavir at -12 hour, 0 hour and 12 hour related to PF-07321332 dosing (Treatment A), and a single oral dose of 300 mg PF-07321332 (2 × 150 mg tablets) under fed conditions and 3 doses of 100 mg ritonavir at -12 hour, 0 hour and 12 hour related to PF-07321332 dosing (Treatment B). There will be a total of 2 treatment sequences shown in [Table 1](#) with the assigned Treatments A or B in each treatment period.

A total of approximately 12 healthy male and/or female participants will be randomly assigned to investigational product such that approximately 6 participants will be enrolled to

each sequence. Participants who withdraw from the study may be replaced at the sponsor's discretion in collaboration with the Investigator.

Each enrolled participant will participate in 2 study periods to receive 2 different treatments according to the sequence determined by randomization:

- Treatment A: Single oral dose of 300 mg PF-07321332 (2 × 150 mg tablets) under fasted conditions and 3 doses of 100 mg ritonavir at -12 hour, 0 hour and 12 hour related to PF-07321332 dosing. (Reference)
- Treatment B: Single oral dose of 300 mg PF-07321332 (2 × 150 mg tablets) under fed conditions and 3 doses of 100 mg ritonavir at -12 hour, 0 hour and 12 hour related to PF-07321332 dosing. (Test)

Participants will be randomly assigned to 1 of 2 sequences as in Table 1. Serial PK samples will be collected at timepoints shown in [SoA](#).

Participants will be discharged on Period 2, following completion of all assessments.

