### **9.5. Sample Size Determination**

Approximately 12 participants will be enrolled in the study. Participants who withdraw from the study may be replaced at the sponsor's discretion in collaboration with the Investigator.

CCI

CCI							

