3.3. Other Endpoint(s)

Blood samples for PK analysis of PF-07321332 will be collected according to the Schedule of Activities given in the protocol.

Plasma PK parameters of PF-07321332 will be derived (as data permit) from the concentration-time data using standard noncompartmental methods. Actual PK sampling times will be used in the derivation of PK parameters. In the case that actual PK sampling times are not available, nominal PK sampling time will be used in the derivation of PK parameters.

Table 3. Noncompartmental PK Parameters of PF-07321332 to be calculated

Parameter	Analysis Scale	PF-07321332
AUC _{inf} *	ln	A, D
AUC _{last}	ln	A, D
C _{max}	ln	A, D
T _{max}	R	D
t _{1/2} *	R	D
CL/F*	ln	D
V _z /F*	ln	D

*=if data permits.

Abbreviations: A = analyzed using a statistical model; D=displayed with descriptive statistics as outlined in Table 4 in Section 6.1; ln=natural-log transformed; R=raw (untransformed)

T_{last} will also be provided as a support parameter for AUC_{last}. T_{last} values will only be listed and not summarized.

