6.1. Primary Endpoint(s)

The plasma PK parameters detailed in Section 3.3 will be listed and summarized for participants in the PK Parameter Set (as defined in Section 4). Missing values will be handled as detailed in Section 5.3. Each PK parameter will be summarized by treatment. Each summary will include the set of summary statistics as specified in Table 4.

Table 4. PK Parameters to be Summarized Descriptively

Parameter	Summary Statistics
AUC _{last} , AUC _{inf} , C _{max} , CL/F and V _z /F	N, arithmetic mean, median, cv%, standard deviation, minimum, maximum, geometric mean and geometric cv%.
T _{max}	N, median, minimum, maximum.
t _{1/2}	N, arithmetic mean, median, standard deviation, minimum, maximum.

For AUC_{inf}, AUC_{last} and C_{max} a listing of the individual participant ratios (Treatment B (fed)/Treatment A (fasted)) will be provided. Box and whisker plots for individual participant parameters (AUC_{inf}, AUC_{last} and C_{max}) will be presented by treatment and overlaid with geometric means.

Supporting data from the estimation of t_{1/2} will be listed by treatment where applicable: terminal phase rate constant (k_{el}); goodness of fit statistic from the log-linear regression (r²); the percent of AUC_{inf} based on extrapolation (AUC_{extrap%}); and the first, last, and number of time points used in the estimation of k_{el}. These data may be included in the CSR.

Presentations for PF-07321332 concentrations will be presented using participants in the PK Concentration Set (as defined in Section 4) and will include:

- a listing of all concentrations sorted by participant ID, treatment and nominal time post-dose. The concentration listing will also include the actual times. Deviations from the nominal time will be given in a separate listing.
- a summary of concentrations by treatment and nominal time post-dose, where the set of statistics will include n, mean, median, standard deviation, coefficient of variation (cv), minimum, maximum and the number of concentrations above the lower limit of quantification.
- individual concentration-time plots by treatment (on both linear and semi-log scales) against actual time post-dose (there will be separate spaghetti plots for each treatment per scale).
- individual concentration-time plots by participant (on both linear and semi-log scales) against actual time post-dose (there will be separate spaghetti plots for each participant per scale).

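### Tmax is summarised only by treatment, so this crossover gives no estimate or interval for a within-participant fed-minus-fasted shift in Tmax

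*Protocol*

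**What the plan says.** Protocol 4.1 describes a "randomized, 2-treatment, 2-sequence, 2-period crossover study to evaluate the effect of a high-fat meal", and Protocol 9.5 states that "Approximately 12 participants will be enrolled in the study". Table 1 of the protocol plans 6 per sequence. Every completer contributes one fed and one fasted Tmax.

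Tmax is a secondary endpoint in Protocol 3 and SAP 2.1. It sits under the objective "To characterize the pharmacokinetic parameters of PF-07321332 boosted with ritonavir following a single oral dose of PF-07321332 in combination with ritonavir".

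For the analysis, Protocol 9.3.1.2 says "The PK parameters listed in Table 2 will be summarized descriptively by treatment". SAP Table 3 uses two codes: "A = analyzed using a statistical model; D=displayed with descriptive statistics as outlined in Table 4 in Section 6.1". AUCinf, AUClast and Cmax carry both codes. Tmax carries D alone, on the raw scale. The Table 4 row for Tmax reads "N, median, minimum, maximum".

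The mixed model with 90% CIs covers AUCinf, AUClast and Cmax. So does the only planned within-participant comparison, for which "a listing of the individual participant ratios (Treatment B (fed)/Treatment A (fasted)) will be provided". SAP 6.2 refers back to 6.1, and SAP 6.3 plans nothing further.

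Individual values are kept: SAP 6.1 says that the PK parameters "will be listed and summarized for participants in the PK Parameter Set (as defined in Section 4"). Concentration-time plots by participant are also planned.

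**The concern.** The study exists to describe what a high-fat meal does to absorption, and Tmax is the endpoint that speaks to timing. A crossover lets each participant act as their own control, and the plan uses this for AUC and Cmax. For Tmax it reports two marginal medians with their ranges. A reader who wants the shift has to subtract one median from the other, with no measure of uncertainty, or work it out from the listings.

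At stake is how precisely and clearly a secondary result is reported. Any interval added after the data have been seen would not be pre-specified.

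**Working it through.** The documents state no Tmax figure, and the basis of the sample size is blacked out, so there is no planned number to reproduce. Three checks apply.

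**1. What is planned for each parameter**

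| | AUCinf, AUClast, Cmax | Tmax |
|---|---|---|
| Individual values listed | yes | yes |
| Summary by treatment | yes | yes |
| Individual fed/fasted comparison listed | yes (ratio) | no |
| Fed-versus-fasted estimate | yes (mixed model) | no |
| Interval | 90% CI | no |

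The SAP does not fill the gap left by Protocol 9.3.1.2.

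**2. Can the planned Tmax row show the paired shift?** The data here are invented, for 12 participants.

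- Fasted: 1, 1, 1.5, 1.5, 2, 2, 2.5, 2.5, 3, 3, 4, 4 h. Median (2 + 2.5)/2 = 2.25 h, range 1 to 4 h.
- Fed: 1.5, 2, 2, 2.5, 2.5, 3, 3, 4, 4, 4, 6, 6 h. Median 3.0 h, range 1.5 to 6 h.
- Difference of medians: 3.0 - 2.25 = 0.75 h.

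Participants alternate between the two sequences. Let D be the period 2 minus period 1 difference in Tmax. In sequence 1 (fasted then fed), D is fed minus fasted plus the period effect. In sequence 2, D is fasted minus fed plus the period effect. Each half-difference (D from sequence 1 minus D from sequence 2)/2 is therefore free of the period effect. With 6 and 6 participants there are 6 x 6 = 36 of them. Their median is the Hodges-Lehmann estimate.

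The interval runs from the 8th to the 29th ordered value. The exact rank-sum tail at U <= 7 is 43/924 = 0.0465, so coverage is 1 - 2 x 43/924 = 90.7%, ignoring ties.

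| Pairing | Planned Table 4 row (fasted; fed) | Hodges-Lehmann | 90.7% interval |
|---|---|---|---|
| In the order shown | 2.25 (1 to 4); 3.0 (1.5 to 6) | 1.0 h | 0.75 to 1.25 h |
| Fed values reversed | identical | 1.0 h | -0.25 to 2.5 h |

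The planned row is the same in both cases, while the precision of the paired shift differs widely.

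The interval remains available after dropout. With 5 and 5 participants, the 5th to 21st of 25 values give 1 - 2 x 12/252 = 90.5%.

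**3. How much precision is at stake?** The documents give no fasted Tmax, variability or correlation, so all inputs are assumptions: 12 participants, log-scale SD 0.4, fasted median 1.5, 2, 2.5 or 3 h, additive shift 0.5, 1, 2 or 3 h, and within-person correlation 0, 0.3 or 0.6. Tmax was rounded to the nearest time in the Schedule of Activities. That gives 4 x 4 x 3 = 48 settings, in which the difference of medians was compared with the 6-versus-6 Hodges-Lehmann estimate.

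- Variance ratio (difference of medians over paired estimate): about 0.8 to 6.2, and above 1 in 45 of 48 settings.
- Root mean squared error: lower for the paired estimate in 45 of 48 settings.
- Coverage of the nominal 90.7% interval: about 90% to 98%, because of ties and rounding.
- Least favourable to the paired estimate: fasted 2 h, shift 2 h, correlation 0. The SDs are 0.34 h (medians) and 0.37 h (paired), and (0.34/0.37)^2 is about 0.8.
- Bias of the difference of medians has no fixed sign. With a fasted median of 2.5 h, a 2 h shift averages about 1.7 h and a 3 h shift about 3.35 h. With a fasted median of 2 h, a 2 h shift averages 1.96 h.

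**The case against.** The strongest reply is that this is a preference. The meal-effect objective is the primary one, and its endpoints are the ratios of AUC and Cmax. Tmax belongs to a separate objective to characterise the pharmacokinetics, alongside half-life, CL/F and V/F, none of which gets a contrast. A descriptive summary by treatment meets that objective. No hypothesis is tested and no decision rule applies (Protocol 9.1, SAP 5.1), so no planned conclusion depends on a Tmax interval. All of this stands, and it sets the severity. It does not supply the missing contrast. AUC and Cmax also receive 90% CIs without any test.

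Four stronger readings are tempting, and the documents do not support them.

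- **That the plan throws the pairing away.** Individual Tmax values are listed and profiles are plotted by participant. The pairing is missing only from the summaries.
- **That Tmax can take only the scheduled times.** Actual sampling times are used, with nominal times as a fallback (Protocol 9.3.1.1, SAP 3.3), and Protocol 8.4.1 tolerates small deviations. The values will cluster near an uneven grid, so near-ties are likely.
- **That the meal delays absorption.** The visible text gives no direction, so the point concerns a shift either way.
- **That the planned medians understate the shift by about 0.3 h.** This appears with a fasted median of 2.5 h and a 2 h shift. It vanishes or reverses under other equally plausible inputs.

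**Conclusion.** The point holds as a low-severity omission in estimation. Neither document plans a within-participant Tmax difference, a fed-minus-fasted estimate or an interval, and the by-treatment summary cannot provide the size or precision of a shift. The protocol and SAP agree with each other here, and the primary analysis is untouched.

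The gap in the outputs follows from the text alone. The size of the precision loss rests on assumed inputs. Across the ranges tried, the difference of medians usually had more variance than the paired estimate (ratio about 0.8 to 6), with a few settings in which it did as well or better. No single ratio or bias figure should be quoted as a property of the plan.

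**What to change.** In SAP 6.1, and in matching form in Protocol 9.3.1.2, add:

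> Individual fed-minus-fasted Tmax differences will be listed. The median difference will be estimated by the Hodges-Lehmann method from the period differences by sequence, with a distribution-free 90% CI (approximate because of ties on the sampling grid). Treatment medians and ranges will also be shown; no hypothesis is tested.

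Only participants with a Tmax in both periods can contribute to the estimate, and the order statistics for the interval follow from the numbers per sequence.

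The cost is a few lines of text and code on data already collected. It needs no extra samples or participants, raises no multiplicity question, and leaves the AUC and Cmax analyses as they are.
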